The primary endpoint in this study is time to resolution of OHE per the HE Grading Instrument (HEGI). OHE status will be evaluated every 12 hours (+/- 2 hours) after randomization. Resolution is defined as a HEGI score < 2.

Statistical Methods:

The primary efficacy endpoint is time to OHE resolution. OHE resolution is defined as a HEGI score < 2. Time to resolution of OHE is defined as the duration between the date/time of first dose of study drug and the date/time of first resolution of OHE. Subjects who complete the blinded randomized treatment period without experiencing OHE resolution will be censored at 14 days post first dose.

The primary efficacy analysis of time to OHE resolution between each active rifaximin SSD plus lactulose treatment group and the placebo plus lactulose group will be tested using the log-rank test.

Analysis of primary efficacy endpoint will be tested in intent-to-treat (ITT) and per protocol (PP) populations.

- The ITT population will include all randomized subjects who received at least one dose of blinded treatment drug.
- The PP population will include all ITT subjects who remain in study through the end of the blinded randomized treatment period and who have not deviated from the protocol in any way likely to seriously affect the primary outcome of the study. Important protocol deviations will be identified prior to locking the study database.

The incidence of treatment-emergent AEs will be summarized for each treatment group by body system and MedDRA preferred term. If a subject reports the same AE more than once, then that subject will only be counted once for the summary of that AE, using the most severe intensity.

The incidence of treatment-emergent AEs of infections, such as spontaneous bacterial peritonitis (SBP), urinary tract infection (UTI), pneumonia, bacteremia and cellulitis, will be summarized by each treatment group. If a subject reports the same AE more than once, then that subject will only be counted once for the summary of that AE, using the most severe intensity. Severity and AE leading to early termination will also be presented for these infection AEs.

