3.0 INTRODUCTION

3.1 Disease Background and Scientific Rationale

3.1.1 Liver Cirrhosis

The magnitude of the health care burden caused by liver disease in the United States (US) is significant from both a societal and health economic perspective. Approximately 2.6 million people have liver disease in the US ([Pleis 2009](#)). In 2004, 2.3 million ambulatory care visits, and 759,000 hospitalizations were needed to care for these patients ([Everhart 2008](#)). Cirrhosis is a major cause of much of the chronic liver disease (CLD) in the US and is the 12th leading cause of death. Using data from the Nationwide Inpatient Sample (NIS) database from 1998 to 2006, a series of 217,948 hospital admissions with a primary diagnosis of cirrhosis was evaluated. Mortality rates from complications of cirrhosis in this series were approximately 8%, 18%, 10%, and 45% for ascites, hepatic encephalopathy (HE), variceal bleeding, and hepatorenal syndrome (HRS), respectively ([Singla 2011](#)). Similarly, other studies have demonstrated that the in-hospital mortality of patients with spontaneous bacterial peritonitis (SBP) ranges from 10% to 50% ([Toledo 1993](#), [Runyon 1991](#), [Rimola 1995](#), [Felisart 1985](#), [Navasa 2013](#), [Gines 1990](#), [Tito 1988](#), [Planas 2004](#)). The incidence of cirrhosis in the US is on the rise and will continue to be a major health burden. The NIS database indicated that cases of cirrhosis increased at an annual rate of 3.7% over the 9-year period studied. It is predicted that over the next 20 years, cases of Hepatitis C Virus (HCV)-related cirrhosis will double ([Davis 2010](#)). This is not unexpected given the current prevalence of chronic HCV infection in the US is 2.7 to 3.9 million people and the fact that the cause of cirrhosis is HCV infection in approximately 26% of cases ([Wolf 2012](#)).

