5.0 STUDY DESIGN

5.1 Description of Study Design

Study RNHE2041 is a Phase 2, randomized, double-blind, placebo controlled, multicenter study evaluating the efficacy and safety of rifaximin SSD tablets (40 mg IR and 80 mg SER) plus lactulose in subjects hospitalized with OHE. Subjects who have liver cirrhosis and OHE, defined as a score of 2 or 3 on the Hepatic Encephalopathy Grading Instrument [[\(HEGI\); Appendix A](#)], are eligible for enrollment. Subjects who successfully meet the inclusion/exclusion criteria will enter the treatment period and will be randomized in a 1:1:1:1:1 ratio into 1 of 5 treatment groups as noted below. The blinded treatment period starts upon randomization following hospital admission.

Subjects will be on blinded treatment for up to 14 days. All subjects who complete the blinded randomized treatment phase (defined as confirmed resolution of OHE), will continue on to the safety follow-up period and receive 30 days of open-label treatment with Xifaxan® 550 mg upon hospital discharge, regardless of the treatment arm to which they were previously randomized. If subjects remain hospitalized following OHE resolution, standard of care treatment (which may include Xifaxan® 550 mg) should be given until hospital discharge. Open-label drug should only be dispensed to subjects upon hospital discharge. Please note this may be on a different day than OHE resolution.

- Treatment A: 40 mg immediate release (IR) rifaximin SSD tablet once daily (QD) and lactulose*.
- Treatment B: 40 mg immediate release (IR) rifaximin SSD tablet twice daily (BID) and lactulose*.

- Treatment C: 80 mg sustained extended release (SER) rifaximin SSD tablet once daily (QD) and lactulose*.
- Treatment D: 80 mg sustained extended release (SER) rifaximin SSD tablet twice daily (BID) and lactulose*.
- Treatment E: SSD placebo tablet twice daily (BID) and lactulose*.

*Oral Lactulose will be administered according to the product label, with dosage adjusted to produce 2 to 3 soft stools daily or per PI discretion. Rectal lactulose may be administered in lieu of oral lactulose. Bristol stool type will still be assessed as required by the protocol for subjects dosed with rectal lactulose. Dose amount and frequency for oral and rectal lactulose should be administered according to the product label or per PI discretion.

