7.2 Statistical Hypothesis

The log-rank test is a statistical method for comparing distributions of time until the occurrence of an event of interest among independent groups. The null hypothesis tested by the log-rank test is that of equal time distribution among groups. Rejection of the null hypothesis indicates that the event rates differ among groups at one or more time points during the study.

$$H_0: S_1(t) = S_2(t)$$

versus the alternative:

$H_A: S_1(t) \neq S_2(t)$ Where $S_1(t)$ and $S_2(t)$ represent the cumulative probability distributions of the times from baseline until the first OHE resolution for each SSD group and the placebo group, respectively.

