7.4 Study Populations

Intent to Treat (ITT): The ITT population will include all randomized subjects who received at least one dose of study drug.

Analysis on the ITT sample will be used as the primary efficacy analysis and will be performed for all efficacy endpoints. Subjects will be analyzed in the treatment group to which they were randomized.

Per Protocol (PP): The PP population will include all ITT subjects who remain in the study through the end of the blinded randomized treatment period and who have not deviated from the protocol in any way likely to seriously affect the primary outcome of the study. Important protocol deviations will be identified prior to locking the study database.

Safety: The safety population will include all subjects who received at least 1 dose of study drug. All subjects in the safety population will be analyzed according to the treatment they actually received.

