7.5.4 Efficacy Endpoint Analyses

Analysis of Primary Efficacy Endpoint

The primary efficacy endpoint is the time to OHE resolution as measured by the HEGI, a modified West Haven Criteria scale. OHE resolution is defined as a HEGI grade of < 2. Resolution of OHE must be confirmed with a repeat evaluation using the HEGI at least 3 and no more than 12 hours after the initial evaluation to demonstrate persistence of resolution. Time to resolution of OHE is defined as the duration between the date/time of first dose of study drug (baseline) and the date/time of first documented resolution of OHE via the HEGI. Subjects who complete the 14 day randomized treatment period without experiencing OHE resolution will be censored at 14 days.

The primary efficacy analysis of time to OHE resolution between each active rifaximin SSD plus lactulose treatment group and the placebo plus lactulose group will be tested using the log-rank test.

Analysis of primary efficacy endpoint will be tested in ITT and PP populations.

Analysis of Secondary Efficacy Endpoints

Analyses of secondary efficacy endpoints will be based on the ITT population.

- Time to OHE resolution defined as a WHC score of 0 or 1
- Time to 1 unit decrease in WHC score during the randomized treatment period.
- Change from Baseline in WHC score at Day 15 or end of blinded treatment period, whichever occurs first.
- Change from Baseline in HEGI score at Day 15 or at end of blinded treatment period, whichever occurs first.
- Time to improvement in HEGI score.
- Length of hospitalization from Baseline to End of Blinded Treatment Phase.

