All Subject assessments will be performed by a trained and qualified Evaluator. Efforts should be made to have the same evaluator assess the same Subject for as many HEGI assessments as possible. Every effort must be made for the same Evaluator to conduct the HEGI assessments at both the resolution of OHE and the confirmation of resolution assessed 3 to 12 hours later.

¹Evaluator, defined by only licensed physicians, physician's assistants or nurse practitioners, who are trained in these instruments may conduct the assessment.

²Assessments are conducted twice per day, approximately 12 hours (±2 hours) apart. Following resolution of OHE, a confirmatory HEGI (3 to 12 hours post initial resolution) must be done to complete the blinded randomized treatment phase.. Subjects should continue to dose on blinded study medication until OHE resolution is confirmed.

³Subject will report on lactulose use (if any) and open-label dosing compliance from previous visit to current visit. Diary cards are not being used on this study.

⁴Open-label Safety Follow-up visits will be conducted by a study investigator.

⁵Clinical laboratory tests run within 24 hours of consent, may be used in place of drawing new labs at Screening provided all protocol required labs are present. Note: AFP is only required at Screening.

⁶ Serum pregnancy test is done at Screening and urine pregnancy test at EOS visit (open-label safety follow-up Visit 3)

⁷ Open-label drug should only be dispensed to subjects upon hospital discharge. Please note this may be on a different day than OHE resolution.

⁸ If a subject early terminates/discontinues during the study, the visit schedule at the end of the that treatment phase should be followed for their ET visit.

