8.1.2 Day 2 up to Day 15: Randomized Treatment Period

The following are to be conducted each day the subject is hospitalized.

Conducted Daily

- Record all concomitant medications and AEs.
- Collect vital sign measurements (include weight, supine blood pressure, heart rate, respiration rate and temperature).
- Collect blood and urine for clinical laboratory tests (hematology, blood chemistry, and urinalysis).
- Dispense study drug and administer dose to subject.
- Record date and times of study drug dose.
- Record date, time(s) and dose(s) of lactulose.
- Record frequency of bowel movements and stool appearance. ([Bristol, Appendix E](#))

Conducted TWICE Daily at 12 Hour (± 2 Hr) Intervals (approx. 7AM and 7PM)

- Complete a full physical examination, including evaluation for complications of liver cirrhosis.
- Determine and record HEGI score. ([Appendix A](#))
- Determine and record WHC score. ([Appendix B](#))

Criteria for OHE Resolution

For the purposes of this clinical study, OHE resolution is determined solely on the HEGI score. A HEGI score of < 2 indicates resolution of OHE, whereas a HEGI score of ≥ 2 indicates a continuation of the OHE episode.

Resolution of the OHE episode (HEGI score of < 2) must be confirmed by a repeat evaluation (HEGI) at least 3 and no more than 12 hours after the initial evaluation to demonstrate persistence of the OHE resolution.

- If the OHE resolution is not confirmed by this repeat evaluation, the subject continues in the study until OHE resolution occurs again and is subsequently confirmed by a repeat evaluation 3-12 hours following.
- If the OHE resolution is confirmed by this repeat evaluation, the subject is considered resolved. Resolution of OHE will be recorded as the date/time of the HEGI assessment immediately prior to the confirmation evaluation. NOTE: Subjects should continue to dose on blinded study medication until OHE resolution is confirmed.

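### The primary log-rank test has no rule for ITT subjects who die, are transplanted or withdraw before confirmed resolution, and the per-protocol set drops them, which selects on outcome

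*Combined protocol and SAP*

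**What the plan says.** Section 7.5.4 compares each active arm with placebo by the log-rank test on time from first dose to confirmed resolution (HEGI below 2). Its one censoring rule is "Subjects who complete the 14 day randomized treatment period without experiencing OHE resolution will be censored at 14 days". The synopsis has the same rule in other words: "Subjects who complete the blinded randomized treatment period without experiencing OHE resolution will be censored at 14 days post first dose".

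Section 7.2 states the null hypothesis through two functions that "represent the cumulative probability distributions of the times from baseline until the first OHE resolution". The same section adds that rejection means the event rates differ at some point in the study.

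Section 7.4 puts every randomized and dosed subject in the ITT set and makes that set primary. Of the per-protocol set it says: "The PP population will include all ITT subjects who remain in the study through the end of the blinded randomized treatment period", and it also requires no serious deviation. The synopsis has the same rule.

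The plan foresees early exits. Section 5.2.1.2 lists withdrawal reasons, with liver transplant as an example. Section 7.5.5 tabulates adverse events with a fatal outcome. Section 8.3.1 lists exit assessments, including a HEGI. None of these sections gives an event or censoring time.

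The word 'complete' has two meanings. Section 5.1 ties it to resolution: "All subjects who complete the blinded randomized treatment phase (defined as confirmed resolution of OHE". Footnote 2 of Table 1 says a confirmatory HEGI "must be done to complete the blinded randomized treatment phase". Section 7.5.4 speaks of completing 14 days without resolution.

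**The concern.** A subject who dies or is transplanted on day 5 without confirmed resolution is in the primary analysis set, but no sentence says what time and status that subject has. Two analysts could follow the text faithfully and run different primary tests. One would censor at day 5. The other would carry the subject as unresolved to day 14.

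The two choices answer different questions. Censoring at exit compares the rate of resolution among those still present. Carrying to day 14 compares the cumulative probability of having resolved. They diverge when exits differ by arm. Section 3.2 gives a reason why they might, since it cites a trial reporting lower mortality on rifaximin plus lactulose.

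The per-protocol set has a separate problem, which comes from a written rule. The blinded period ends at confirmed resolution or at 14 days, so a subject who leaves before its end cannot have a confirmed resolution. Removing such subjects removes only people without the event and raises the apparent resolution rate most in the arm that loses most.

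**Working it through.** **The plan's own figure.** Section 7.3 gives 76% versus 51% resolution by day 14, two-sided 0.05, at least 80% power and 61 evaluable per group. Freedman's formula with 76% and 51% entered as event-free proportions gives HR = ln 0.76 / ln 0.51 = 0.408. Events = ((1 + HR)/(1 − HR))² × (1.960 + 0.842)² = 44.3, and 44.3 / (0.24 + 0.49) = 60.7, so 61. With resolution as the event, HR = ln 0.24 / ln 0.49 = 2.00 and the same formula gives 56. Either way, at least 80% holds at 61. The figure contains no rule for exits.

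**Assumed inputs.** The documents state no exit rate. I use 4/65 = 6.2%, anchored only on 65 enrolled against 61 evaluable, and double that, 8/65 = 12.3%. Half of exits are taken as death or transplant.

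**Why deletion misleads.** Take equal true resolution of 51%, with exits of 12.3% active and 6.2% placebo. Among those who stay, the resolved proportion is 0.51/(1 − 0.123) = 58.2% active and 0.51/(1 − 0.062) = 54.3% placebo. An apparent advantage of about 4 points comes from deletion alone.

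**Why exit-censoring shifts the question.** With constant hazards, the 14-day resolution hazard is −ln(1 − r − e) × r/(r + e), where r is resolution and e is exit.
- Active: −ln(0.367) × 0.51/0.633 = 0.808.
- Placebo: −ln(0.428) × 0.51/0.572 = 0.756.
- Ratio: 1.068, although both arms resolve 51%.

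**Simulation.** 65 per arm, HEGI on a 12-hour grid to day 14, 60,000 replicates, one comparison with placebo, one-sided rejection at z > 1.96 (false superiority in the direction of active). The ranges span two timing models: truncated-exponential times at 0.25/day, and constant hazards. 'Proposed' keeps deaths and transplants unresolved to day 14 and censors other exits at the last HEGI. Entries are percentages.

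| Resolution, active/placebo | Exits, active/placebo | Exit-censored | Proposed | All leavers kept to day 14 | Leavers deleted |
|---|---|---|---|---|---|
| 51/51 | 12.3/6.2 | 4.2–4.7 | 3.2–3.6 | 2.4–2.8 | 6.0–6.6 |
| 51/51 | 6.2/12.3 | 1.3–1.4 | 1.7–1.9 | 2.3–2.6 | 0.8–0.9 |
| 51/51 | 6.2/6.2 | about 2.5 | about 2.5 | about 2.4 | about 2.5 |
| 76/51 | 6.2/12.3 | 78.5–86.6 | 80.7–87.5 | 82.5–88.0 | 73.3–81.9 |
| 76/51 | 6.2/6.2 | 85.5–92.2 | 83.9–90.8 | 82.3–89.2 | 86.1–92.4 |

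The first three rows are error rates (nominal 2.5%) and the last two are power. In the first row, two-sided rejection is roughly 7–8% with leavers deleted and about 6% exit-censored, against 5%. In the fourth row, deletion costs 78.5 − 73.3 = 5.2 or 86.6 − 81.9 = 4.7 points against exit-censoring. In the last row, exit-censoring and the proposed rule reach different verdicts in 2.4–3.4% of comparisons.

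**Stress test.** All exits are deaths, 9% active and 18% placebo, resolution 76%/51%. Power is 76–86% exit-censored, 82–88% proposed and 67–78% deleted. The 18% is borrowed from the inpatient series in section 3.1.1 and is not a 14-day trial rate.

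**The case against.** A reader might infer that the primary analysis does not test its stated hypothesis. The documents do not support that. Exit-censoring is written nowhere. For withdrawals unrelated to prognosis it is a valid way to test equal time-to-resolution distributions. It also fits the event-rates sentence in section 7.2. With balanced exits, error is nominal under every rule.

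A reader might also infer that a HEGI below 2 at exit, without its repeat, has no status. It does. Section 7.5.4 requires confirmation, and section 8.1.2 says "If the OHE resolution is confirmed by this repeat evaluation, the subject is considered resolved". An unconfirmed reading is therefore not an event, and only the censoring time is missing.

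Materiality is a fair challenge. At 6.2% exits with half of them deaths or transplants, the rule affects about two subjects per arm (65 × 0.062 × 0.5 = 2.0). If exits are fewer on active, as the mortality result cited in section 3.2 suggests, exit-censoring is conservative. The 18% mortality figure has no time frame and comes from a broader population. This trial excludes sepsis and hepatocellular carcinoma and requires unassisted swallowing.

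Finally, counting death as non-resolution is a choice of estimand. If resolution hazards are equal and only exits differ (6.2% active, 12.3% placebo), the proposed rule favours active in 3.3% of trials and exit-censoring in 2.4%. Cumulative resolution then truly differs (51.0% versus 48.9%), so the proposed rule suits the cumulative wording and exit-censoring suits the rates wording. Section 7.2 contains both, which is a reason to state the choice.

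These points limit the claim about the primary test. They do not answer the missing rule or the per-protocol deletion.

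**Conclusion.** The point holds in limited form, and the plan should be changed. The primary analysis lacks a rule for subjects who leave before confirmed resolution. For deaths and transplants, the unwritten choice changes what is tested when exits differ by arm. In the unequal-exit scenarios in the table, the choice between exit-censoring and the proposed rule moves one-sided error by roughly 0.4 to 1.1 points and power by 0.8 to 2.2 points. The effect is larger only if deaths are frequent and unequal.

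The per-protocol rule is the firmer finding because it is written and its direction is known. It raises one-sided false superiority to 6.0–6.6% when the active arm loses more subjects, and costs about 5 power points when placebo loses more.

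Every size here depends on assumed exit rates, an assumed half share of deaths and transplants, and two simple timing models. The gap and the selection on outcome follow from the text alone.

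The censoring sentences also need reconciling with the definition of completion. If completing means confirmed resolution, the synopsis sentence applies to nobody.

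**What to change.** 1. In section 7.4 and the synopsis, do not exclude a subject from the per-protocol set solely for dying or leaving unresolved.
2. In section 7.5.4 and the synopsis, count death or transplant before confirmed resolution and within 14 days of first dose as not resolved, censored at day 14. Apply this also when the death or transplant is known to follow an earlier withdrawal, so that no subject fits two rules.
3. Censor other withdrawals at the last HEGI.
4. Add two sensitivity analyses: one keeps all unresolved leavers to day 14, the other censors all of them at exit. The first covers adverse-event and worsening-condition exits that may be informative.
5. Reconcile 'complete' in the synopsis, sections 5.1, 5.5 and 8.4, and Table 1 footnote 2 with the 14-day period in section 7.5.4.

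The change is mostly wording. Exit HEGI, deaths and withdrawal reasons are already collected. However, the list in section 5.2.1.2 has no separate category for death or transplant, so their dates must be identifiable in the analysis data.

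The statistical cost against exit-censoring is 1.4–1.6 power points at equal 6.2% exits with half of them death or transplant (0.8–2.3 points if that share is 25–75%). If 18% died in both arms it would be 6–11 points. The rule should be fixed before the unblinded interim look in section 7.6.

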Treatment with rifaximin IR and SER SSD was shown to be safe and well-tolerated and demonstrated potential therapeutic utility, particularly the IR 40 mg QHS and SER 80 mg QHS formulas, in preventing complications of liver cirrhosis and all-cause mortality in patients with early liver decompensation.

While the primary analysis did not demonstrate statistically significant differences in time to composite endpoint of hospitalization for the liver cirrhosis complications or mortality up to 24 weeks for the combined rifaximin SSD groups versus placebo ($p = 0.8062$) or any pairwise comparison, in a post-hoc analyses there was a consistent pattern of benefit with rifaximin SSD IR 40 mg and SSD SER 80 mg.

The IR 40 mg group post-hoc analysis revealed a statistically significant difference versus placebo ($p = 0.0297$) for the composite endpoint of all-cause hospitalization/all-cause mortality (primary endpoint of the study was hospitalization for any of the liver cirrhosis complications (HE, EVB, SBP, or HRS) ([RNLC2131 CSR Appendix 16.1.13](#))). In addition, subjects in the alcohol-induced only subgroup had a statistically significant difference in time to All-cause Hospitalization/All-cause Mortality versus placebo when treated with rifaximin IR 40 mg QHS ($p = 0.0298$). Furthermore, subjects with a Conn score of 0 demonstrated a statistically significant difference for both the overall treatment comparison of any rifaximin SSD treatment versus placebo and predominantly in favor of the IR 40 mg formulation.

Results of the sensitivity analysis on the PP population demonstrated a statistically significant difference in the time to hospitalization for any of the liver cirrhosis complications or all-cause mortality up to 24 weeks that was in favor of the SER 80 mg QHS treatment group versus placebo ($p = 0.0464$). Based on the Kaplan-Meier estimates, the SER 80 mg QHS group presented with the highest survival rate of all treatment groups for Time to Hospitalization for Any of the Liver Cirrhosis Complications by Treatment Group, however this effect was not statistically significant.

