This characteristic makes the new SSD formulation particularly attractive for use in a population with significantly impaired hepatic function. Data from early phase trials with the SSD formulation support the safety, solubility and potential clinical utility of rifaximin in preventing complications of cirrhosis in patients with early liver decompensation. Based on these data and the medical need for safe and effective treatments for OHE, the Sponsor is seeking to initiate clinical development of Rifaximin SSD in OHE.

The current standard of care for patients with hepatic encephalopathy is treatment with nonabsorbable disaccharides lactulose or lactitol, which decreases the absorption of ammonia through cathartic effects and by altering colonic pH. In addition to lactulose, oral antibiotics have been used in OHE to reduce ammonia-producing enteric bacteria. However, because of side effects these agents are only infrequently used at present.

Rifaximin is currently approved for reduction in risk of OHE recurrence, but not for the treatment of OHE. Randomized clinical trials showing the superiority of rifaximin plus lactulose versus lactulose alone suggest that rifaximin may be useful in the treatment of OHE. Based on these data and the need for safe and effective alternatives to systemic broad spectrum antibiotics used to treat complications of cirrhosis, this Phase 2 dose-ranging trial will be conducted to assess the viability of rifaximin SSD for the prevention of complications in cirrhosis patients with early decompensation.

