4.0 OBJECTIVES

4.1 Efficacy Objectives

4.1.1 Primary Objective

The primary objective of this study is to assess the efficacy of rifaximin SSD [40 mg immediate release (IR) and 80 mg sustained extended release (SER)] plus lactulose versus placebo plus lactulose for the treatment of OHE.

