7.3 Sample Size

Approximately 325 subjects will be randomized in 1:1:1:1:1 ratio to rifaximin SSD tablets [40 mg immediate release (IR)] QD plus lactulose, rifaximin SSD tablets [40 mg immediate release (IR)] BID plus lactulose, rifaximin SSD tablets [80 mg sustained

extended release (SER)] QD plus lactulose, rifaximin SSD tablets [80 mg sustained extended release (SER)] BID plus lactulose and placebo BID plus lactulose.

The sample size estimation is based on cumulative probability distributions of the times from baseline until the first OHE resolution (HEGI score <2) between treatment groups using the log-rank test.

This sample size estimation is based on a previous study with rifaximin ([Sharma 2013](#)). It is assumed that approximately 76% of rifaximin plus lactulose subjects and 51% of placebo plus lactulose subjects will experience OHE resolution over the course of up to 14 days of treatment. With two-sided type I error rate of 0.05, approximately 61 evaluable subjects per treatment group will provide at least 80% power to demonstrate the superiority of rifaximin SSD to placebo using the log-rank test.

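### Four unadjusted primary tests share one placebo arm, so a claim that rifaximin SSD as a product is superior would not carry the stated 0.05 error rate

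*Combined protocol and SAP*

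**What the plan says.** Section 7.5.4, and the Statistical Methods part of the synopsis, define "The primary efficacy analysis of time to OHE resolution between each active rifaximin SSD plus lactulose treatment group and the placebo plus lactulose group" as a log-rank comparison. Section 7.2 writes the null and alternative hypotheses "for each SSD group and the placebo group, respectively". With four active regimens randomised 1:1:1:1:1 alongside one placebo arm, that is four primary tests. Section 7.4 makes the ITT analysis primary, so the per-protocol analysis adds no further primary test.

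The error rate appears only in the sample-size text (section 7.3, repeated in the synopsis): "With two-sided type I error rate of 0.05, approximately 61 evaluable subjects per treatment group will provide at least 80% power". The same sentence then gives the aim that this power serves: "demonstrate the superiority of rifaximin SSD to placebo using the log-rank test". The error rate is not labelled as per comparison or family-wise, and section 7.5.4 gives no significance level. Neither the synopsis nor section 7 gives a multiplicity adjustment, a testing order, a pooled or global test, or a statement that unadjusted testing is intended. Section 3.4.2 describes the trial's purpose: "this Phase 2 dose-ranging trial will be conducted to assess the viability of rifaximin SSD".

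**The concern.** The plan does not say what counts as success for the product: one named regimen, any regimen, or all of them. The tests concern regimens; the power sentence concerns rifaximin SSD. If one of the four comparisons gives p < 0.05, a reader can take the power sentence as licence to say that rifaximin SSD beat placebo at the 5% level. That claim means that at least one regimen is effective, and its error rate is that of the best of four tests, not of one. The level that governs it should be fixed before unblinding.

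**Working it through.** **Inputs.** Two-sided alpha 0.05, 61 evaluable per arm, and 76% versus 51% resolved by 14 days (section 7.3); 65 per arm planned (section 5.2); four comparisons with equal arms and one placebo group (sections 7.2, 7.3 and 7.5.4).

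**1. The plan's own figure.** Under proportional hazards the hazard ratio for resolution is ln(1 - 0.76)/ln(1 - 0.51) = 2.00. Events per comparison at 61 per arm: 61 x (0.76 + 0.51) = 77.5. The expected test statistic (drift) is:
- Schoenfeld: sqrt(77.5) x ln(2.00)/2 = 3.052; power = Phi(3.052 - 1.960) = 86.3%.
- Freedman: sqrt(77.5) x (2.00 - 1)/(2.00 + 1) = 2.935; power = Phi(2.935 - 1.960) = 83.5%.

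The claim of at least 80% power is therefore true for one comparison at an unadjusted 0.05. At the level needed for family-wise control (critical value 2.442, step 3), the same drifts give Phi(2.935 - 2.442) = 68.9% and Phi(3.052 - 2.442) = 72.9%. The sizing therefore fits a per-comparison 0.05.

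The exact figure of 61 comes from Freedman's formula if 76% and 51% are entered as proportions *without* the event: hazard ratio ln(0.51)/ln(0.76) = 2.454; n = 7.849 x (3.454/1.454)^2 / 0.73 = 60.7, rounded up to 61. Section 7.3 defines those percentages as resolving, so this only suggests where 61 came from and is not used for power below. On the plan's own definition 80% needs 66 events, 66/1.27 = 52 per arm (Schoenfeld), or 71 events, 71/1.27 = 56 per arm (Freedman).

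**2. Error over four tests when no regimen works.** Equal arms and a shared control give correlation 0.5 between test statistics; write s = sqrt(0.5).
- Any two-sided p < 0.05: 1 - integral of phi(x) [Phi((1.96 + s x)/s) - Phi((-1.96 + s x)/s)]^4 dx = 15.6%.
- Any false superiority: 1 - integral of phi(x) Phi((1.96 + s x)/s)^4 dx = 7.8%.

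Simulated log-rank tests at 65 per arm give 15.8% and 7.7%. Independent tests would give 1 - 0.95^4 = 18.5% and 1 - 0.975^4 = 9.6%, so the shared placebo arm lowers the figures somewhat. A single test has 2.5% in the favourable direction; 7.8/2.5 is about 3.1.

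**3. What adjustment requires.** Step-down Dunnett critical values with four, three, two and one hypotheses remaining are 2.442, 2.349, 2.212 and 1.960. The first corresponds to an unadjusted p of 0.0146. Putting 2.442 into the integrals of step 2 returns 5.0% and 2.5%.

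**4. Power under the plan's 76% versus 51%.** Drifts are 2.935 to 3.052 at 61 per arm, and 3.030 to 3.150 at 65 (65 x 1.27 = 82.6 events). Each range runs from Freedman to Schoenfeld. The adjusted figures come from multivariate normal draws with correlation 0.5.

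| Power per regimen | 61 per arm | 65 per arm |
|---|---|---|
| Unadjusted | 83-86% | 86-88% |
| Step-down Dunnett, all four work | 77-81% | 80-83% |
| Step-down Dunnett, only one works | 69-73% | 72-76% |

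A product-level claim needs only one regimen to clear 2.442. If all four work, that probability at 61 per arm is 1 - integral of phi(x) Phi((2.442 - drift + s x)/s)^4 dx = 92-94%. If only one works, it is in effect the last row of the table.

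**The case against.** The strongest reply is that nothing is wrong. The hypotheses are written per group, the sizing is per group at 0.05, and a Phase 2 dose-ranging trial need not control family-wise error. All of that stands, so neither the 0.05 nor the sample size is called an error here. A second reply is that rifaximin SSD in the power sentence is simply the drug's generic name, not a decision rule. That is fair as far as it goes. But it is the only sentence that links an error rate to superiority, and no other sentence says what a positive trial is. A third reply is that pairwise p-values cannot address a product claim. They can once the claim is defined as at least one effective regimen, because that is the hypothesis a family-wise procedure protects.

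Three stronger readings are tempting, and the documents do not support them:
- *That family-wise control at 80% power per regimen, and hence a larger trial, is required.* In Phase 2 that is a trade-off for the sponsor, not a defect.
- *That section 3.3.1 foretells how this trial will be reported.* A reader might infer this from "there was a consistent pattern of benefit with rifaximin SSD IR 40 mg and SSD SER 80 mg" after a non-significant primary analysis. That section concerns another trial with a different endpoint and population, states the failed primary result openly (p = 0.8062), and labels the later findings as post-hoc or per-protocol. It says nothing about reporting here.
- *That the primary objective overlooks the four regimens.* Its wording, "assess the efficacy of rifaximin SSD [40 mg immediate release (IR) and 80 mg sustained extended release (SER)] plus lactulose versus placebo plus lactulose", names two formulations, but sections 5.1, 5.5 and 7.3 list all four regimens.

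**Conclusion.** The point holds in a limited form. Each of the four planned tests is sound at two-sided 0.05 for its own regimen. A statement that rifaximin SSD as a product is superior, resting on any one significant regimen, would be false 7.8% of the time when no regimen works, about three times the 2.5% of a single test. The plan contains nothing that would correct this.

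The error rates rest on equal arms, a shared control and the normal approximation, and simulation of the log-rank test supports them. The powers also assume proportional hazards, the plan's 76% and 51%, and no dropout; early censoring or a delayed effect would lower them. The point matters for what may be concluded, not for how the trial is run, and it is worth acting on because the remedy is cheap.

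**What to change.** In section 7.5.4, add that multiplicity-adjusted p-values for the four ITT log-rank tests (for example step-down Dunnett) will be reported beside the unadjusted ones. State that an unadjusted result supports a conclusion about that regimen only. State also that any claim that rifaximin SSD as a product is superior, meaning that at least one regimen is effective, requires an adjusted p below 0.05 in its favour.

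In section 7.3 and the synopsis, reword the power sentence to refer to superiority of a given rifaximin SSD regimen to placebo, at two-sided 0.05 per comparison.

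The cost is a few sentences and one column of p-values. No planned test, arm or sample size changes, and the unadjusted power per regimen is untouched. The downside is that a product-level claim becomes harder to reach, by the amounts in the power table, most noticeably if only one regimen works.
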